(http://www.healthmeasures.net/images/PROMIS/manuals/PROMIS_Physical_Function_Scoring_Manual.pdf).
4. PROMIS Sleep Disturbance Short Form. The PROMIS Sleep Disturbance short form is a convenient 6-item scale that correlates strongly with the longer forms. It shows greater measurement precision for assessing sleep disturbance than other commonly-used (and much longer) questionnaires such as the Pittsburgh Sleep Quality Index and the Epworth Sleepiness Scale; its brevity and convenience are a major advantage for both research and clinical settings (Yu et al, 2011). The PROMIS Sleep Disturbance Scale is expressed as a T-score, with a population mean of 50 and SD of 10. Possible T scores in this distribution range from 31.7 to 76.1; higher scores represent a greater disruption of sleep (i.e., lower sleep quality).
5. Patient Health Questionnaire (PHQ) – Depression. The 2-item PHQ-2 is a brief depression screening tool that correlates strongly with PHQ-9 scores and shows good sensitivity for identifying individuals with depressive disorders in the general population and in a variety of medical samples (Arroll et al, 2010). Scores range from 0-6, with higher scores indicating more depressive symptomatology.
6. Generalized Anxiety Disorder – 2 item scale (GAD-2). The GAD-2 is a 2-item screening tool that is widely used to screen for clinically significant anxiety symptoms and anxiety disorders in clinical settings. It shows good sensitivity and specificity as a screening tool for anxiety disorders (Kroenke et al, 2007). Scores range from 0-6, with higher scores indicating more anxiety symptomatology.
7. Tobacco, Alcohol, Prescription medication, and other Substance use Tool (TAPS-1). The TAPS-1 is the screening component of the TAPS tool and consists of a single stem question with four items covering frequency of past-12-month use of tobacco, alcohol, illicit drugs, and non-medical use of prescription medications. Scores range from 0-4; higher scores indicate a higher likelihood of problematic substance use. The TAPS-1 shows good sensitivity and specificity for identifying substance use disorders (Gryczynski, et al, 2017).

8. Opioid Use Questionnaire (OUQ). The OUQ is an indicator of past or present use of any of the listed opioid medications. There are a total of three yes/no items where a yes indicates the use of such medications.

F.2.6. Blinding Procedures

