## 4.2 Secondary Objectives

The secondary objectives of this study are to evaluate the effect of CNTX-6970 (300mg BID) on general pain-related measures, including physical and psychosocial functioning, as well as biomarkers of pain and inflammation. This objective is addressed by the following specific aims:

**Aim 3:** Assess the efficacy of CNTX-6970 (300mg BID) in comparison to placebo with respect to secondary outcome measures related to OA on the knee: (a) WOMAC-C (function subscale) (Bellamy *et al.*, 1988); (b) Hospital Anxiety and Depression Scale (HADS) (Zigmond and Snaith, 1983); (c) Patient Global Impression of Change (PGIC) (Kroenke *et al.*, 2019); (d) PROMIS Sleep Disturbance Scale – 6A (Yu *et al.*, 2011); (e) Sleep Duration Question; and (f) Daily Knee Pain Intensity on a 0-10 Numeric Rating Scale (NRS).

**HYPOTHESIS 2:** CNTX-6970 300mg BID will be superior to placebo with respect to symptoms measured by (a) WOMAC-C (function subscale); (b) Hospital Anxiety and Depression Scale (HADS); (c) Patient Global Impression of Change (PGIC); (d) PROMIS Sleep Disturbance Scale– 6A; (e) Sleep Duration Question; and (f) Daily Knee Pain Intensity on a 0-10 NRS.

**Aim 4:** Assess the efficacy of CNTX-6970 (300mg BID) in comparison to placebo with respect to general outcomes of pain: (a) Pain Catastrophizing Scale –Short Form 6 (Sullivan *et al.*, 1995); (b) PROMIS Physical Functioning Short-Form 6b (Schalet *et al.*, 2016); (c) Patient Health Questionnaire – 2 item scale (PHQ-2) – Depression (Arroll *et al.*, 2010); (d) Generalized Anxiety Disorder – 2 item scale (GAD-2) (Kroenke *et al.*, 2007; Plummer *et al.*, 2016); (e) Tobacco, Alcohol, Prescription medication, and other Substance use Tool (TAPS-1) (Gryczynski *et al.*, 2017); and (f) Opioid Use Questionnaire (OUQ).

**HYPOTHESIS 3:** CNTX-6970 300mg BID will be superior to placebo with respect to outcomes measured by (a) Pain Catastrophizing Scale –Short Form 6; (b) PROMIS Physical Functioning Short-Form 6b; (c) Patient Health Questionnaire (PHQ) – Depression; (d) Generalized Anxiety Disorder – 2 item scale (GAD-2) and (e) Tobacco, Alcohol, Prescription medication, and other Substance use Tool (TAPS-1); and (f) Opioid Use Questionnaire.

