- PROMIS Physical Functioning Short-Form 6b (Schalet *et al.*, 2016). The PROMIS Physical Functioning short form is a 6-item scale that is widely used in pain research. It is a unidimensional scale that shows broad coverage of the physical function construct, good construct validity, and high levels of temporal stability (Schalet *et al.*, 2016). The PROMIS Physical Function Scale is expressed as a T-score, with a population mean of 50 and SD of 10. Higher scores represent better physical functioning; possible T scores in this distribution range from 21 to 59.
- Sleep Duration Question. A single-item scale measuring the duration of actual sleep a participant has gotten, on average, over the past month. Numerical responses will be provided in hours and minutes.
- Pain Health Questionnaire (PHQ) – Depression (Arroll *et al.*, 2010). The 2-item PHQ-2 is a brief depression screening tool that correlates strongly with PHQ-9 scores and shows good sensitivity for identifying individuals with depressive disorders in the general population and in a variety of medical

samples (Arroll *et al.*, 2010). Scores range from 0-6, with higher scores indicating more depressive symptomatology.

- Generalized Anxiety Disorder – 2 item scale (GAD-2) (Kroenke *et al.*, 2007; Plummer *et al.*, 2016). The GAD-2 is a 2-item screening tool that is widely used to screen for clinically significant anxiety symptoms and anxiety disorders in clinical settings. It shows good sensitivity and specificity as a screening tool for anxiety disorders (Kroenke *et al.*, 2007). Scores range from 0-6, with higher scores indicating more anxiety symptomatology.
- Tobacco, Alcohol, Prescription medication, and other Substance use Tool (TAPS-1) (Gryczynski *et al.*, 2017). The TAPS-1 is the screening component of the TAPS tool and consists of a single stem question with four items covering frequency of past-12-month use of tobacco, alcohol, and illicit drugs, and non-medical use of prescription medications. Scores range from 0-4; higher scores indicate a higher likelihood of problematic substance use. The TAPS-1 shows good sensitivity and specificity for identifying substance use disorders (Gryczynski *et al.*, 2017).
- Opioid Use Questionnaire (OUQ). The OUQ is an indicator of past or present use of any of the listed opioid medications. There are a total of three yes/no items where a yes indicates the use of such medications.

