## 5 Study Methods

### 5.1 General Study Design and Plan

This is a multi-crossover design with 2 blocks and 2 periods per block. Each period lasts 6 weeks. Patients will be randomized to one of the treatment sequences shown in Figure 1. The Schedule of Events Table in

the Protocol gives the timing of the outcome assessments. In general, we will be analyzing the data on an intent-to-treat basis (ITT).

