## 5.3 Randomization and Blinding

For entry into the study and randomization, all eligibility criteria MUST be met (i.e., all inclusion criteria and no exclusion criteria specified in the protocol). Patients who meet inclusion/exclusion criteria at the Baseline Visit (day 0) will be randomized. After documentation of written informed consent and the screening period, clinical sites will confirm eligibility and complete randomization by accessing the Almac's centralized web-based system for randomization and drug management - the Interactive Web Response System (IXRS). Subjects will be randomized equally between treatment sequences shown in Figure 1: Drug:Placebo:Placebo:Drug or Placebo:Drug:Drug:Placebo. A standard block randomization will be used, stratifying by K-L grade (stratum 1 K-L grade 1 or 2, and stratum 2 K-L grade 3 or 4) to achieve balance on randomization sequences. The randomization will be implemented by the IXRS vendor in consultation with the study statisticians. After Randomization, drug will be dispensed.

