For PGIC, this instrument asks if the overall pain since the start of the study is “Very much improved” (score 0), “Much improved” (score 1), “Minimally improved” (score 2), “No Change” (score 3), “Minimally worse” (score 4), “Much worse” (score 5), “Very much worse” (score 6). The analysis for outcome (c) PGIC will use a proportional odds regression with outcome PGIC at week 24 (V9), controlling for treatment, age, sex and baseline WOMAC-A; this model will not control for week 3 PGIC since the instrument is asking about the change in pain. Note also that the treatment in the last period is the same treatment as in the first period, so a comparison of the active to the placebo in terms of change in pain can be done using week 24 PGIC outcomes for the two different treatment sequences used in this trial. The analysis plan for outcome (e) will follow the same approach as in aim 4 below.

**Aim 4.** Outcomes (a)-(f) are assessed at baseline and week 24. Testing hypotheses for these outcomes will not benefit from the multi-period crossover design because they are assessed only at baseline and week 24. Instead, we will test the hypotheses by comparing subjects taking active drug versus placebo at the last treatment period ending on week 24. Regressions will be used to model the outcome at week 24 as a function of treatment, the baseline level of the outcome, age, sex and K-L Grade. A standard linear regression will be used for continuous outcomes; a proportional odds model will be used for the non-binary ordinal outcomes defined by discrete categories (e.g., PHQ-2, GAD) and logistic regression models will be used for binary outcomes (e.g., OUQ).

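### TAPS-1 recalls the past 12 months, so for 24-week completers both sequences have equal drug and placebo time in the window, and the planned test of Hypothesis 3(e) does not estimate drug versus placebo

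*SAP*

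**What the plan says.** Both documents define TAPS-1 by a 12-month recall. SAP 4.4.3 gives it as "frequency of past-12-month use of tobacco, alcohol, and illicit drugs", and Protocol F.2.5 as "frequency of past-12-month use of tobacco, alcohol, illicit drugs"; each adds non-medical use of prescription medications. The score runs from 0 to 4. The Schedule of Events and SAP 4.4.3 place it at baseline and week 24/ET only.

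Hypothesis 3 (Protocol C.2, SAP 4.2) lists TAPS-1 as item (e) among the outcomes on which the drug will be superior. Because these outcomes are measured only twice, SAP 9.2 says of Aim 4 that "we will test the hypotheses by comparing subjects taking active drug versus placebo at the last treatment period ending on week 24", with regression on treatment, the baseline value, age, sex and K-L grade. Protocol K.2 describes the same comparison.

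On the design, SAP 5.1 states "Each period lasts 6 weeks", and SAP 5.3 gives the only two sequences as "Drug:Placebo:Placebo:Drug or Placebo:Drug:Drug:Placebo" (DPPD and PDDP below), with equal allocation.

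Neither document shortens or re-anchors the TAPS-1 recall period at week 24.

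**The concern.** The Aim 4 model labels a patient as drug or placebo by what was taken in weeks 18 to 24. That label suits an outcome describing the patient's state at week 24 or over the last few weeks. TAPS-1 describes a year. By week 24 every completer has taken both treatments for equal time inside that year, and more than half of the year precedes randomization. The two groups being compared differ in the order of exposure, not in its amount.

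SAP section 7 says that treatment effects will be reported with 95% confidence intervals whether or not the null is rejected. For TAPS-1, that interval would carry the label of a drug-versus-placebo effect on substance use without estimating one. A result near zero could be taken as evidence of no effect, and a result away from zero as evidence of one. Neither reading would be sound.

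**Working it through.** **The plan's own figure.** The documents give no sample size, effect size or power for TAPS-1. The only stated figure that bears on the week-24 comparison is the number completing all four periods (SAP section 6): 55 × 0.85⁴ = 28.71, which reproduces the stated 29.

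**Inputs.** Recall window of 12 months, taken as 52 weeks (SAP 4.4.3, Protocol F.2.5). Four periods of 6 weeks, 24 weeks in all (SAP 5.1). Sequences DPPD and PDDP (SAP 5.3). Assessment at week 24 (SAP 9.2).

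**Content of the window at week 24.**

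| Sequence | Drug weeks | Placebo weeks | Pre-study weeks | Total |
|---|---|---|---|---|
| DPPD | 6 + 6 = 12 | 6 + 6 = 12 | 52 − 24 = 28 | 52 |
| PDDP | 6 + 6 = 12 | 6 + 6 = 12 | 52 − 24 = 28 | 52 |

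The difference in drug exposure is 0 of 52 weeks. The last period is 6/52 = 11.5% of the window. The pre-study part is 28/52 = 54% and lies within the baseline window as well.

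**What the contrast estimates.** Let e₁ to e₄ be the drug's effect on weekly use if drug is taken in period 1 to 4, and let the score be mean use over the window. The expected difference, last-period drug (DPPD) minus last-period placebo (PDDP), is

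6 × (e₁ + e₄ − e₂ − e₃) / 52.

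If the effect is the same in every period, this is 0. If it builds up, so that the second consecutive drug period in PDDP has effect (1 + b)e and the other drug periods have e, the contrast is 6 × (2e − e − (1 + b)e)/52 = −6be/52. That is not zero, but its sign is opposite to the drug's effect.

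**Look-back length.** The share of the window on which the two sequences differ in drug exposure at week 24 is:

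- 4 or 6 weeks: 100% (all drug in DPPD, all placebo in PDDP)
- 12 weeks: 0 (6 drug and 6 placebo in both)
- 24 weeks: 0 (12 and 12 in both)
- 52 weeks: 0 (12, 12 and 28 pre-study in both)

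**Simulation check.** Assumptions, none of them from the documents: between-person SD 1, weekly SD 1, score equal to mean use over the window, no carryover, baseline-adjusted linear comparison, two-sided alpha 0.05, 4,000 runs per setting.

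- 52-week look-back, true effects of 0, 0.5, 1 and 2 SD: mean estimate 0.00 and rejection between 4.6% and 5.4%, at both n = 29 and n = 55. Simulation error is about ±1.96 × √(0.05 × 0.95/4000) = ±0.7 points, so rejection is at the nominal level throughout.
- 6-week look-back, true effect 0.5 SD: mean estimate −0.50, rejection 63% at n = 29 and 91% at n = 55.

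Under these assumptions the failure comes from the look-back, not the sample size.

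**Early termination.** If TAPS-1 is taken at an ET visit at a period end, the sequences differ by 6 drug weeks at week 6 (6 against 0), by 0 at week 12 (6 against 6), and by 6 at week 18 (6 against 12). The largest difference is 6/52 = 11.5% of the window.

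**The case against.** **The SAP already concedes a limitation.** SAP 9.2 says that the Aim 4 outcomes gain nothing from the crossover design. That concedes lost efficiency; it does not address a recall window that spans all four periods.

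**Exact cancellation is conditional.** This stands. A reader might infer that the contrast is zero whatever the drug does. The documents do not support that. Zero requires 24-week completion and effects that add over weeks without carryover or build-up. PDDP gives 12 consecutive drug weeks and DPPD two separate spells of 6, so an effect that grows with continuous use, or that lasts more than six weeks after stopping, can leave a non-zero contrast. The simulation result depends on the same conditions.

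**A significant result need not be only chance or recall.** This also stands. Carryover and order effects are possible too. Recency of recall could bring in some last-period signal, but of unknown weight. None of these yields the drug-versus-placebo difference that Hypothesis 3(e) names.

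**Not everyone completes.** At the planned dropout, about 55 − 29 = 26 patients would not, and Protocol F.3.2 moves their final assessments to an earlier period end. Exposure can then be unequal, but the Aim 4 comparison is written for the period ending at week 24, so this does not rescue it.

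**The OUQ.** A reader might extend the point to Hypothesis 3(f), since SAP 4.4.3 says "The OUQ is an indicator of past or present use of any of the listed opioid medications". The documents give only that it has three yes/no items, with no item wording, look-back or split between past and present use. A present-use item could fall within the last period, so the OUQ is not included. The Sleep Duration Question asks about the past month, which fits inside the last 6 weeks, and does not share the problem.

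**The consequence is small.** P-values are unadjusted, estimation is ranked above testing, and no stated decision rests on TAPS-1. This limits the severity, but not the mismatch between instrument and test.

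**Conclusion.** The point holds for TAPS-1. For patients who complete 24 weeks, the Hypothesis 3(e) test compares two groups with identical totals in the recall window: 12 weeks of drug, 12 of placebo and 28 pre-study. The treatment label refers to 11.5% of that window. The exposure count follows from the design and needs no assumption about effect size; it takes 12 months as 52 weeks.

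The planned contrast therefore does not estimate drug versus placebo. Under additive effects without carryover or build-up, its expected value is zero and its power equals alpha. Outside those conditions it may differ from zero, but it still does not measure the hypothesised difference.

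Severity is minor. One unadjusted secondary outcome is affected. The WOMAC-A primary analysis is not, and the finding does not by itself condemn the other Hypothesis 3 outcomes.

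**What to change.** Remove TAPS-1 from the Hypothesis 3 superiority tests in Protocol C.2 and K.2 and in SAP 4.2 and 9.2. Report it descriptively at baseline and week 24/ET, with a sentence explaining that the 12-month window spans both treatments in both sequences. Keep collecting it as a common data element.

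The cost is wording in two documents and one fewer hypothesis test. Data collection, the visit schedule and the sample size do not change.

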## 5 Study Methods

### 5.1 General Study Design and Plan

This is a multi-crossover design with 2 blocks and 2 periods per block. Each period lasts 6 weeks. Patients will be randomized to one of the treatment sequences shown in Figure 1. The Schedule of Events Table in

the Protocol gives the timing of the outcome assessments. In general, we will be analyzing the data on an intent-to-treat basis (ITT).

## 5.2 Inclusion and Exclusion Criteria and General Study Population

Specifics on the inclusion/exclusion criteria are provided in the protocol. Subjects must complete at least 5 NRS's throughout the entire screening period. The following is blinded inclusion criteria not listed in the protocol:

- The standard deviation of these End of Day Pain Ratings (for average pain over the last 24 hours) from the screening period must be less than or equal to 1.2.
- Left Knee Average WOMAC Score range must be 20-45 (calculated average of pain scores across screening timepoints) *OR* Right Knee Average WOMAC Score range must be 20-45 (calculated average of pain scores across screening timepoints). These requirements will be reviewed and approved by CCC staff before the SAFER interview is scheduled.

The rationale for excluding individuals with high variability in their daily average pain measures, as determined by their NRS responses during the first week of screening, is to not include individuals with unreliable pain measures and not include individuals prone to high placebo response (Farrar *et al.*, 2014).

## 5.3 Randomization and Blinding

For entry into the study and randomization, all eligibility criteria MUST be met (i.e., all inclusion criteria and no exclusion criteria specified in the protocol). Patients who meet inclusion/exclusion criteria at the Baseline Visit (day 0) will be randomized. After documentation of written informed consent and the screening period, clinical sites will confirm eligibility and complete randomization by accessing the Almac's centralized web-based system for randomization and drug management - the Interactive Web Response System (IXRS). Subjects will be randomized equally between treatment sequences shown in Figure 1: Drug:Placebo:Placebo:Drug or Placebo:Drug:Drug:Placebo. A standard block randomization will be used, stratifying by K-L grade (stratum 1 K-L grade 1 or 2, and stratum 2 K-L grade 3 or 4) to achieve balance on randomization sequences. The randomization will be implemented by the IXRS vendor in consultation with the study statisticians. After Randomization, drug will be dispensed.

### Blinding Procedures

Eligible subjects will be randomized through the IXRS. Blinding will be assured by restricting access of site and Sponsor personnel and/or designees to the randomization sequences, and by providing identical tablets and packaging for the placebo and 300 mg CNTX-6970 tablets. For the final analysis, randomization sequences for all subjects will be released after all subjects have completed the study and the clinical database is locked. For the DSMB safety reviews, the randomization sequences will be released to an independent statistician and a programmer to produce unblinded reports. The Sponsor and the Investigators will remain blinded.

Unblinding of individual randomization sequences during the study is discouraged. The Investigator at a site may break the blind for a given subject in the event of a medical emergency, where knowledge of the subject's randomization sequence must be known in order to facilitate appropriate emergency medical treatment. The Investigator should attempt to contact the study Medical Monitor before unblinding a subject's randomization sequence identity in order to obtain concurrence that unblinding a subject's randomization sequence is necessary. If not reasonable prior to unblinding, investigators should notify the Medical Monitor as soon as possible after an unblinding event. Once unblinded, a subject must be permanently withdrawn from study participation.

## 6 Sample Size

The sample size for this study was determined based on the primary efficacy aim to detect clinically meaningful and realistic effects of CNTX-6970 (300 mg BID) compared to placebo in the multi-period crossover

design model. Power was computed for effect sizes ranging from 0.25 to 0.50 using Monte Carlo simulation. Data were simulated from multi-period crossover models with block, period, and carryover effects, and varying within and between subject variability.

Although carryover effects can be efficiently isolated and estimated in the analysis stage by using the mixed-effects models proposed in Section 7, power for the primary hypothesis was computed using only WOMAC-A assessed during the last 2 of 6 weeks per treatment period to minimize carryover effects. The power of the test depends on the relationship of the between-subject variability to the within-subject variability. In general, the between-subject variability is larger than the within-subject variability, but a range of Between/Within (B/W) variance ratios (5/1, 2/1) were investigated. With a sample size of  $n = 55$  per arm, using a two-sided Type I error rate of  $\alpha = 0.05$ , the power to detect an effect size (for the active treatment vs. placebo) of Cohen's  $d = 0.35$  exceeds 95% when the ratio  $B/W = 2/1$ .

Assuming a 15% early termination (e.g., dropout) rate during each of the 4 periods will yield a sample size of approximately  $n = 29$  with complete observations at all treatment periods. If we conservatively assume that only subjects with complete data will be analyzed, the corresponding power with  $n = 29$  exceeds 80% when the ratio  $B/W = 2/1$  with an effect size as low as 0.30. Figure 2 shows the results of a simulation study to evaluate the power of this design. Because we will use all available data from all enrolled subjects in the analysis, the actual power in the case of 15% early termination per treatment period will be larger than what Figure 2 shows. If the ratio B/W is larger than 2, say B/W=3, 4 or 5, the power for detecting the treatment effects is much larger. For example, with only 29 participants, if B/W=5, the power to detect an effect of magnitude Cohen's  $d = 0.35$  exceeds 0.95. Note that the reported test-retest reliability of the WOMAC-A measure is 0.86, which corresponds to a  $B/W = 7$ .

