the relationship of the between-subject variability to the within-subject variability. In general, the between-subject variability is larger than the within-subject variability, but we investigated a range of Between/Within (B/W) variance ratios (5/1, 2/1). With a total sample size of $n=55$, there will be more than adequate power for the study using a two-sided Type I error rate of $\alpha=0.05$. A power analysis was conducted with $n=50$ and the power to detect an effect size (for an active treatment vs. placebo) of Cohen's $d=0.35$ is approximately 95% when the ratio B/W=2/1. Assuming a 15% early termination rate during each of the 4 periods will yield a sample size of $n=26$ with complete observations at all treatment periods for this simulation. If we conservatively assume that only subjects with complete data will be analyzed, the corresponding power with $n=26$ is approximately 81%. Because we will use all available data from all enrolled subjects in the analysis, the actual power in the case of 15% early termination rate per treatment period will be larger than 81%, and anywhere between 81% and 95%. If the ratio B/W is larger than 2, say B/W=3, 4 or 5, the power for detecting the treatment effects is much larger. For example, with only 26 patients, if B/W=5, the power to detect an effect of magnitude Cohen's $d=0.35$ is 0.96. Note that the reported test-retest reliability of the WOMAC-A measure is 0.86, which corresponds to a B/W=7.

[figure not shown]

Figure 2: Power versus Cohen's d effect size. B/W indicates the ratio of between-subject to within-subject variance of the WOMAC-A measure. Assuming that only data from completers will be used in the analysis gives a lower bound of the power that can be achieved for the given range of effect sizes.

■ PUBLICATION POLICY

See EPPIC-Net Publication Policy.

■ REFERENCES

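### Protocol K.4 and SAP section 6 give completer powers at B/W = 2 that one simulation cannot both produce, and both equate a reliability of 0.86 with the wrong B/W

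*SAP*

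**What the plan says.** Both sections report a Monte Carlo study of the multi-period crossover with block, period and carryover effects. Both use effect sizes from 0.25 to 0.50, WOMAC-A from the last 2 of 6 weeks in each period, B/W of 2 and 5, two-sided alpha of 0.05, and 15% loss in each of four periods.

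- **Protocol K.4, B/W = 2.** The total is 55, but the worked example uses 50 and gives about 95% power at d = 0.35. Dropout "will yield a sample size of $n=26$ with complete observations at all treatment periods for this simulation", and "the corresponding power with $n=26$ is approximately 81" percent. The effect size is not repeated in that sentence; I read it as still 0.35.
- **SAP section 6, B/W = 2.** Power at n = 55 and d = 0.35 exceeds 95%. With 29 completers it exceeds 80% "with an effect size as low as 0.30".
- **B/W = 5.** The Protocol says "with only 26 patients, if B/W=5, the power to detect an effect of magnitude Cohen's $d=0.35$ is 0.96". The SAP has "For example, with only 29 participants, if B/W=5, the power to detect an effect of magnitude" 0.35 exceeding 0.95.
- **Reliability.** The SAP says "Note that the reported test-retest reliability of the WOMAC-A measure is 0.86, which corresponds to a" B/W of 7. The Protocol cites the same 0.86, "which corresponds to a B/W=7".
- **Sample size label.** The SAP attaches its 55 to "per arm, using a two-sided Type I error rate of" 0.05. Protocol E.2, Protocol K.4 and the SAP Figure 2 caption treat 55 as the whole sample.

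**The concern.** The SAP has three more completers than the Protocol's example but a smaller effect, 0.30 against 0.35. Three extra patients do not make up for that reduction, yet the stated power hardly changes. If the settings are common, at least one of the B/W = 2 completer figures is wrong. If they are not, neither document says what changed.

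These figures are the stated justification for the sample size. As the text stands, a reader cannot tell which effect the completers would detect with 80% power. The reliability statement is a plain arithmetic slip made in both documents. It is used to suggest that the true B/W lies well above the simulated values. The per-arm label could be read as implying a trial of 2 × 55 = 110.

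**Working it through.** **Completers.** 55 × 0.85⁴ = 28.7, so 29. 50 × 0.85⁴ = 26.1, so 26. Both stated numbers reproduce, and the first confirms that 55 is a total.

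**Method.** Power = Φ(NCP − 1.960), so a stated power implies NCP = 1.960 + z(power). At fixed B/W and common settings, NCP is taken as proportional to d√n. The unstated carryover size, residual correlation and standardizing SD then cancel from the comparison.

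- Protocol point: 0.35 × √26 = 1.785
- SAP point: 0.30 × √29 = 1.616
- Ratio: 1.616/1.785 = 0.905, or 9.5% smaller

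**Scaling between stated figures at B/W = 2.**

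| Stated figure used as anchor | n=29, d=0.30 | n=26, d=0.35 | n=50, d=0.35 | n=55, d=0.35 |
|---|---|---|---|---|
| Protocol, 81% at n=26, d=0.35 | 72.9% | 81% | 97.6% | 98.5% |
| SAP, 80% at n=29, d=0.30 | 80% | 87.2% | 99.0% | 99.4% |
| Protocol, 95% at n=50, d=0.35 | 65.3% | 73.9% | 95% | 96.6% |

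First row, first cell: NCP = 1.960 + 0.878 = 2.838; 2.838 × 0.905 = 2.569; Φ(2.569 − 1.960) = 72.9%.

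On the Protocol's 81%, the effect detectable with 80% power at n = 29 is 0.327, and d = 0.30 would need about 35 completers.

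**Rounding.** Reading approximately 81% as anything from 80% to 82% gives 71.8% to 74.0% at the SAP's point.

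**Trial settings, to see whether any reconcile the pair.** These settings are assumptions, since the documents do not give them.

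- One independent value per period and d on the total SD: the variance of the active-minus-placebo contrast is 1/(1 + 2) = 1/3. The SAP's point gives NCP = 0.30 × √(29 × 3) = 2.80 and power 79.9%, close to its stated figure. The same settings give 87.1% at the Protocol's point.
- Two weekly values with AR(1) correlation 0.7 and d on the between-subject SD: 81.7% at the Protocol's point, 73.7% at the SAP's.
- Unmodelled carryover of 0.1 or 0.2 widened the gap in every setting simulated. With one value per period and a t-test, the SAP and Protocol points were 76.7% and 84.2% at zero carryover, and 44.0% and 56.3% at 0.2.

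**Simulation noise.** The number of replicates is not stated, so a range is shown. The last column is the largest probability, over any common NCP scale, of observing at most 82% at the Protocol's point together with more than 80% at the SAP's.

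| Replicates (assumed) | SE of one power near 81% | Probability of both statements |
|---|---|---|
| 100 | 3.9 points | 5.5% |
| 200 | 2.8 points | 2.4% |
| 500 | 1.75 points | 0.3% |
| 1,000 | 1.24 points | 0.01% |

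**B/W = 5.** Scaling 0.96 at n = 26 to n = 29 gives 97.5%, which agrees with the SAP. The conflict is confined to B/W = 2.

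**Reliability.** Both Figure 2 captions define B/W as between-subject over within-subject variance. With reliability 0.86 this is 0.86/0.14 = 6.14 (5.9 to 6.4 if 0.86 is rounded). B/W = 7 requires 7/8 = 0.875. The ratio of total to within variance, 1/0.14 = 7.14, is near 7 but is not the quantity defined.

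**The case against.** The strongest reply is that the conflict rests on proportional scaling within a shared run, and that the Protocol's own example does not obey it. NCP divided by d√n is 1.457 for the Protocol at n = 50, 1.590 for the Protocol at n = 26, and 1.734 for the SAP at n = 29. The step inside the Protocol is about as large as the step between the documents. K.4 also ties its figures to an n = 50 exercise, so two different runs are likely. This stands in part. The projected powers are approximate, and the noise probabilities depend on the same scaling. But a change of n is already allowed for in d√n, the Protocol's other anchor makes the gap larger (65.3%), and neither document reports different settings.

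Some settings can also be partly inferred. Weekly WOMAC-A over the last 2 weeks suggests two values per period, the SAP's analysis model has AR(1) errors, and Protocol D.1 mentions carryover of 0 to 0.2 for design simulations. None of these is tied to the power figures in K.4 or SAP section 6. Figure 2 is not visible in the text available to me and may show more, but a figure would not reconcile two conflicting written values.

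Finally, no decision turns on this. Completer power is presented as a lower bound, all available data will be analyzed, and every patient in a crossover receives both treatments, so the per-arm wording has a harmless reading. That is fair, and it limits the weight of the point.

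**Conclusion.** The point holds and should be corrected before the analysis. Under one set of settings, about 81% at n = 26, d = 0.35 and more than 80% at n = 29, d = 0.30 cannot both be right. The discrepancy is about 6 to 7 percentage points, or an 80%-power effect of 0.33 against 0.30 at 29 completers. Rounding does not explain it. Monte Carlo error could explain part of it if replicates were few, but is unlikely to explain all. The documents do not allow one to say which figure is off. The comparison assumes common settings, d = 0.35 for the Protocol's completer figure, and NCP proportional to d√n.

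B/W = 7 is wrong in both documents; 0.86 gives about 6.1. The per-arm label is leftover wording: Protocol C.4 and F.3.3.1 use arm for a drug cohort, and only one such cohort remains under study.

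The consequence is limited. Nothing here suggests that the trial is underpowered: power at n = 55, d = 0.35, B/W = 2 is 96.6% or more on every stated anchor, and 6.1 still exceeds both simulated ratios.

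**What to change.** - Run one simulation at n = 55 and n = 29, for B/W of 2 and 5. State the carryover size, residual correlation, number of WOMAC-A values per period, the SD that standardizes d, and the number of replicates.
- Put the same power figures in SAP section 6 and Protocol K.4, without presuming which current figure is right. Replace the n = 50 and n = 26 example in K.4.
- Change the B/W for a reliability of 0.86 from 7 to about 6.1 in both documents.
- In SAP section 6, describe 55 as the total sample size. In K.4, replace the reference to each dose with the single 300 mg BID dose that the protocol now tests.

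The cost is one simulation re-run and wording edits. The number of patients and the analysis do not change. A stated power may come out slightly less favourable.
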